### 4.3. Exclusion Criteria

- Inability to give informed consent

### 4.4. Recruitment of participants

Participants will be recruited from the network of clinics at the Rare Lung Disease-Clinic Network (RLD-CN). The RLDC is a collection of 30 LAM foundation clinics in US and 19 worldwide. These clinics are a hub of many of the rare lung disease we wish to study. A survey of the clinic directors at the RLD-CN suggests that there are over 300 patients with BHD and greater than 700 patients with PLCH being followed currently in this network. In addition, we will seek assistance from the patient advocacy partners such as the BHD Foundation and the Histiocytosis Association to help with recruitment. We will also present our study to patients at national and regional meetings to encourage recruitment. For example, we will take our questionnaires to the International BHD symposium in September 2015 at Syracuse, NY to enable participants to enroll in the study and complete questionnaires at the conference.

### 4.5. Participant Retention

This study does not require follow-up after completion of the survey, however participants may be contacted in the future to verify and update the contact information they provided for the registry.

### 4.6. Data Elements

Data elements for this study include the following information about study participants:

- Contact information
- Demographics
- Age, gender, ethnicity
- Medical history
- Patient reported elements of diagnostic criteria and other clinical manifestations
- Surveillance information for associated clinical anomalies, such as renal tumors in BHD
- Evaluation of dyspnea, other pulmonary problems and need for supplemental oxygen

- Family history
- Smoking history
- Pneumothorax information (diagnosis, management, measures to prevent prevention such as pleurodesis, relationship with flights)
- Flight history
- Effect of pneumothoraces on attitudes towards undertaking air travel
- Pulmonary function tests
- CT scans

#### **4.7. Schedule of Events**

September 2015: Distribute links and paper copies of the questionnaires

November 2015: Resend links and surveys to increase recruitment

January 2016: Data Analysis

April 2016: Manuscript submission

April 2017: Contact patients and start obtaining medical records

November 2017: Data Analysis

April 2018: Manuscript submission

## **5.0 Data and Safety Monitoring Plan**

The study protocol will be reviewed and approved by the National Institutes of Health (NIH) before submission to the University of Cincinnati's IRB and the University of South Florida (USF) for approval. Participant enrollment may only begin with IRB approved consent forms. This is an observational study that meets the federal definition of minimal risk.

Since this is a survey based registry study, traditional study monitoring will not occur. We do not expect any adverse events (AEs) nor will we solicit them. If participants contact USF to report an adverse reaction to participation on this registry, USF will report the adverse event to the USF IRB and the Consortium. Otherwise patients will not be solicited for adverse events. The questionnaire data will be stored in a password protected electronic format in REDCap. Only the investigators will have access to the data files. Paper files will be kept in a locked cabinet in a locked office.

The medical records will only be obtained after getting the required permissions from the patients. Since no intervention is being planned for the participants, there will be minimal risk, and we do not expect any adverse effects. The patient records will be kept in a locked cabinet at all times, and access restricted only to the study personnel.

### **5.1. Study Oversight**

The Study Chair has primary oversight responsibility of this study.

### **5.2. Definitions and Standards**

The Rare Diseases Clinical Research Network defines an adverse event as: "...an unfavorable and unintended sign, symptom or disease associated with a participant's participation in a Rare Diseases Clinical Research Network study."

Serious adverse events include those events that: "result in death; are life-threatening; require inpatient hospitalization or prolongation of existing hospitalization; create persistent or significant disability/incapacity, or a congenital anomaly/birth defects."

An unexpected adverse event is defined as any adverse experience...the specificity or severity of which is not consistent with the risks of information described in the protocol.

Expected adverse events are those that are identified in the research protocol as having been previously associated with or having the potential to arise as a consequence of participation in the study

All reported adverse events will be classified using the Common Terminology Criteria for Adverse Events (CTCAE) developed and maintained by CTEP at National Cancer Institute. Only those events associated with the conduct of the study and as defined above are reportable.

### **5.3. Reporting Timeline**

Within **24 hours** (of learning of the event), investigators must report any reportable Serious Adverse Event (SAE) that:

Is considered life-threatening/disabling or results in death of subject

-OR-

Is Unexpected/Unanticipated

Investigators must report all other reportable SAEs within **5 working days** (of learning of the event).

All other (suspected) reportable AEs must be reported to the RDCRN within **20 working days** of the notification of the event or of the site becoming aware of the event.

Local institutional reporting requirements to IRBs, any CRU oversight committee and the FDA, if appropriate, remain the responsibility of the treating physician and the Study Chair.

#### **5.4. RDCRN Adverse Event Data Management System (AEDAMS)**

Upon entry of a serious adverse event, the DMCC created Adverse Event Data Management System (AEDAMS) will immediately notify the Study Chair, site PIs, the Medical Review Officer, and any additional agencies of any reported adverse events via email.

**Serious adverse events:** The committee appointed Medical Review Officer (MRO) determines causality (definitely not related, probably not related, possibly related, probably related, definitely related) of the adverse event. The MRO may request changes to the protocol or consent form as a consequence of the adverse event. A back-up notification system is in place so that any delays in review by the MRO beyond a specified period of time are forwarded to a secondary reviewer. The Adverse Event Data Management System (AEDAMS) maintains audit trails and stores data (and data updated) and communication related to any adverse event in the study. The DMCC will post aggregate reports of all adverse events (serious/not serious and expected, unexpected) for site investigators and IRBs.

#### **5.5. Known Risks/Discomforts Associated with Study and Procedures**

There is a risk of breach of confidentiality. The risks of completing the questionnaires include fatigue, anxiety and the perception on the part of the patient that questions may be too personal. The patients will be informed in the consent that they can skip any questions they like, or opt out of the questionnaire portion of studies.

#### **5.6. Study Discontinuation (Observational)**

This study will not have study discontinuation rules as it is a survey based registry study. The NIH and local IRBs (at their local site) have the authority to stop or suspend this trial at any time.

#### **5.7. Subject Discontinuation**

All data acquired prior to termination for the reasons outlined below will be included in the primary analysis unless patient withdraws consent.

- Withdrawal of consent
- Withdrawal by the participant
- Withdrawal by the investigator

#### **5.8. Data Quality and Monitoring Measures**

As much as possible data quality is assessed at the data entry point using intelligent on-line data entry via visual basic designed screen forms. Data element constraints, whether independent range and/or format limitations or 'relative' referential integrity limitations, can be enforced by all methods employed for data input. QA reports assess data quality post-data entry. As we note, data quality begins with the design of the data collection forms and procedures and incorporates reasonable checks to minimize transcription and omission errors. Of the more important quality assurance measures are the internal validity checks for reasonableness and consistency.

- Data Monitoring: The RDCRN DMCC identifies missing or unclear data and generates a data query to the consortium administrator contact.
- Data Delinquency Tracking: The Data Management and Coordinating Center will monitor data delinquency on an ongoing basis.

## **6.0 Statistical Considerations**

Data from all surveys will be pooled together. The rate of pneumothorax will be estimated as a percentage of the number of flights taken. We will compare other disease and patient characteristics to try to determine factors associated with an increased risk of in-flight pneumothorax. All analyses will be done by using SAS for Windows, version 9.4, Cary, NC.

NIH Approved 02-28-17

## **7.0 Data Management**

All study data will be collected via systems created in collaboration with the RDCRN Data Management and Coordinating Center and will comply with all applicable guidelines regarding patient confidentiality and data integrity.

### **7.1. Data Management Responsibilities**

Data to be obtained for each study participant in this study will be collected via REDCap. This data will subsequently be transmitted to the DMCC at the University of South Florida by distinct mechanisms using methods that are set forth by DMCC.

*Confidentiality:* Only investigators and other key personnel involved in the study will have access to individually identifiable private information about human subjects.

### **7.2. Data Entry**

Data collection for this study will be accomplished with online electronic case report forms. Using encrypted communication links, on-line forms will be developed that contain the requisite data fields.

## **8.0 Human Subjects**

### **8.1. GCP Statement**

This study will be conducted in accordance with the ethical principles that have their origin in the Declaration of Helsinki, and that are consistent with Good Clinical Practice and all applicable regulatory requirements.

### **8.2. Risks**

All efforts will be made to ensure that the data is secure and the privacy is maintained. There is a risk of breach of confidentiality. The risks of completing the questionnaires include fatigue, anxiety and the perception on the part of the patient that questions may be too personal. The patients will be informed in the consent that they can skip any questions they like, or opt out of the questionnaire portion of studies.

### **8.3. Benefits**

There are no direct benefits for participants from their involvement in this study. The answers obtained from these studies could potentially help patients through informing clinical recommendations, for example, weighing the risk of travel given the risk of developing a pneumothorax associated with air travel. No compensation or incentives will be provided.

### **8.4. Recruitment**

Patients with BHD and PLCH will be recruited with the help of the RLD-CN and the respective patient advocacy groups, the BHD Foundation and the Histiocytosis Association. We expect to enroll over 100 patients with BHD and over 200 patients with PLCH in this study. Adult patients (18 years and older) will be eligible to participate in the study.

### **8.5. Written Informed Consent**

Written informed consent will be obtained from each participant before participation in the study. For the online survey, the informed consent portion will immediately precede the survey in REDCap. Participants will be able to begin the survey only after certifying that they have read and understood the informed consent for the study.

For those using paper forms, the participant's willingness to participate in the study will be documented in writing in a consent form, which will be signed by the participant with the date of that signature indicated. The investigator will keep the original signed consent forms and copies will be given to the participants.

### **8.6. Process of Consent**

Subjects are required to sign an informed consent prior to undertaking the survey in accordance with International Conference on Harmonization (ICH) E6; 4.8, "Informed Consent of Trial Subjects."

It will be clearly explained to the participants that they are free to refuse entry into the study and free to withdraw from the study at any time without prejudice to future treatment. Written and/or oral information about the study in a language understandable by the participant will be given to all participants

## 10.0 Appendices

### Appendix 1. Protocol Amendment History

Date	Protocol Version	Summary of Changes
02-23-17	Amendment 1	

• Re-contact patients with BHD and PLCH who gave us permission to contact them again for future studies

• Obtain permission to gather pulmonary function tests and CT chests

• Correlate PFT data and cyst features with the risk of spontaneous pneumothoraces

• Add [name] as a co-investigator to the protocol

• Updated statistician to [name]

Assessment of Safety of Air Travel in Patients with Birt-Hogg-Dube Syndrome

NCT03040115

Statistical analysis plan

Document date: August 5, 2015

The rate of pneumothorax will be estimated as a percentage of the number of flights taken. Because retrospective distinction between persistent and recurrent pneumothorax can be problematic, all ipsilateral pneumothoraces reported within the same month will be considered as one episode. If a given pneumothorax was treated with more than one intervention (e.g., chest tube followed by chemical pleurodesis followed by surgical pleurodesis), the most aggressive intervention (e.g., in this case, surgical pleurodesis) will be listed as the treatment of record for that event. For the purpose of our study, a pneumothorax that happened either during an air flight or within 24 hours after a flight will be defined as flight-related pneumothorax. We will compare other disease and patient characteristics to try to determine factors associated with an increased risk of in-flight pneumothorax. Statistical significance will be set at P value of 0.05 and determined by the chi-square test and the z-statistic, as appropriate. All analyses will be done by using SAS for Windows, version 9.4, Cary, NC.

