## 1.0 Overview

### 1.1. Protocol Synopsis

Protocol Number:	5714
Protocol Title:	Assessment of Safety of Air Travel in Patients with Diffuse Cystic Lung Disease
Study Chair:	[name]
Statistician:	[name]
Consortium:	Rare Lung Diseases
Participating Sites:	University of Cincinnati
Activation Date:	December 4, 2015
Sample Size:	300 subjects - 100 with Birt-Hogg-Dubé Syndrome (BHD), 200 with Pulmonary Langerhans Cell Histiocytosis (PLCH)
Target Enrollment Period:	September 2015 – September 2016
Study Design:	This is a questionnaire-based study of patients with diffuse cystic lung diseases (DCLDs) to gather information relevant to safety of air travel, especially pertaining to the risk of pneumothorax associated with air travel. In addition, this study will be used to further characterize clinical aspects of disease and establish a contact registry for patients.
Primary Study Objective(s):	To define the risk of pneumothorax associated with air travel in patients with DCLD.
Secondary Study Objective(s):	

• To establish a contact registry for patients with BHD and PLCH

• To define the clinical phenotype of each DCLD in their respective cohort of patients

• To define current screening practices for surveillance of disease-specific anomalies (i.e. renal tumors in BHD)

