	
The study will enroll participants through the clinic network at the Rare Lung Disease Consortium (RLDC) and through the BHD and PLCH foundation websites. Participants will have access to the questionnaire via REDCap (an online data management system) and each participant will be provided a link to complete the survey. In case of lack of internet access or inability to complete the online questionnaire, a paper survey will be mailed out with a pre-paid envelope to return the survey.
 
Inclusion Criteria:
 

• Adult, age 18 or older

• English literate

• Signed, dated informed consent; either given electronically or via paper form

• Diagnosis of BHD, or PLCH as defined by accepted clinical, histopathological and/or genetic criteria.

➢ For BHD, diagnosis would include the presence of fibrofolliculomas/trichodiscomas on skin biopsy, or the presence of pathogenic FLCN mutations.

➢ For PLCH, it would include characteristic radiographic findings and tissue biopsy consistent with PLCH (presence of CD1a positive Langerhans cells or stellate fibrosis in late stages).

 
Exclusion Criteria:
 

• Inability to give informed consent

Outcome Measures:	Number of pneumothoraces associated with air travel, estimated as a percentage of the number of flights taken.
Statistical Considerations (sample size and analysis plan):	Data from all surveys will be pooled together. The rate of pneumothorax will be estimated as a percentage of the number of flights taken. We will compare other disease and patient characteristics to try to determine factors associated with an increased risk of in-flight pneumothorax.
Variables collected	
 
• Contact information
 
• Demographics
 
• Age, gender, ethnicity
 
• Medical history
 
• Diagnosis
 
• Surveillance information for associated clinical anomalies, such as renal tumors in BHD
 
• Evaluation of dyspnea, other pulmonary problems and need for supplemental oxygen
 
• Family history
 
• Smoking history
 
• Pneumothorax information (diagnosis, management, measures to prevent prevention such as pleurodesis, relationship with flights)
 
• Flight history
 
• Effect of pneumothoraces on attitudes towards undertaking air travel
 

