## **2.0 Specific Aims (Hypothesis and Objectives)**

### **2.1. Hypothesis**

The hypothesis to be tested is that air travel is safe in patients with diffuse cystic lung diseases, and there is no increased risk of pneumothorax in this disease population related to air travel.

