### **2.2. Objectives**

1. To define the risk of pneumothorax related to air travel in patients with BHD and PLCH.
2. To establish a contact registry for patients with BHD and PLCH, in order to facilitate participation in future trials.
3. To describe the demographic and clinical characteristics of patients with BHD and PLCH, as well as ascertain clinical practices related to management and surveillance of related medical conditions, such as surveillance of renal tumors in patients with BHD.
4. To determine the relationship between lung function, and radiographic cyst characteristics and the risk of spontaneous pneumothorax in patients with BHD and PLCH.

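### Does the risk-factor analysis use an undefined 'in-flight' event in place of the 'flight-related' event that the SAP defines?

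*SAP*

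**What the plan says.** The SAP gives one operational definition of the event: "a pneumothorax that happened either during an air flight or within 24 hours after a flight will be defined as flight-related pneumothorax". It has two limbs, onset during the flight and onset in the 24 hours after it. The next SAP sentence describes a comparison of patient and disease characteristics to look for "factors associated with an increased risk of in-flight pneumothorax". Protocol Section 6.0 and the statistical row of the synopsis (Section 1.1) contain the same risk-factor sentence: "to try to determine factors associated with an increased risk of in-flight pneumothorax".

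The rate sentence is also the same in the SAP, Protocol Section 6.0 and the synopsis: "The rate of pneumothorax will be estimated as a percentage of the number of flights taken". It names the event without a qualifier. The synopsis row for outcome measures is more specific: "Number of pneumothoraces associated with air travel, estimated as a percentage of the number of flights taken".

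The primary objective in the synopsis is "To define the risk of pneumothorax associated with air travel in patients with DCLD". Section 2.2 repeats it for the two diseases, and the hypothesis in Section 2.1 is that "there is no increased risk of pneumothorax in this disease population related to air travel".

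**The concern.** A SAP that defines an event should use the defined term in its analyses. Here the term appears only in its own definition, and the following sentence uses a different word with a narrower ordinary meaning. Taken literally, 'in-flight' keeps the first limb of the definition and drops the second. A pneumothorax with onset some hours after landing would then be flight-related by definition but absent from the risk-factor comparison. The rate and the comparison would describe different sets of events, and the choice between a narrow and a broad outcome could be made after the data were seen.

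Three side issues add to the impression of looseness. The rate sentence does not name its numerator, while Objective 4 in Section 2.2 introduces spontaneous pneumothorax as a further outcome. The Protocol gives no time window tied to flights. The SAP's title covers BHD only, although the study also enrols PLCH patients and Protocol Section 6.0 pools all surveys.

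**Working it through.** The plan gives no event rate, power or effect size for this outcome, so there is no figure to reproduce. The check is of wording.

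**Count of terms**

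| Term | Uses | Where | Defined? |
|---|---|---|---|
| 'flight-related' | 1 | SAP, in the definition | yes |
| 'in-flight' | 3 | SAP; Protocol Section 6.0; synopsis | no |
| 24-hour window tied to flights | 1 | SAP | – |

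The only other mention of 24 hours is the deadline for reporting serious adverse events in Protocol Section 5.3, which is unrelated.

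**Could 'in-flight' be a separate, narrower event?** Suppose the rate uses the defined event and the risk-factor sentence does not. The SAP would then move to a second event in the very next sentence, with no definition, no announcement of a subset and no reason. Suppose instead that every analysis sentence is read literally. The definition would then serve no analysis at all, although the SAP makes it for the study as a whole. Both readings are strained. Reading 'in-flight' as a short form of the event just defined gives a coherent plan and agrees with the objectives and hypothesis, which speak of air travel.

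**Is the rate's numerator in doubt?** The outcome-measures row pairs pneumothoraces associated with air travel with the same denominator as the rate sentence, the number of flights. A percentage of flights also makes sense only if each counted event is tied to a flight. The SAP then supplies the rule for that tie. Objective 4 does not disturb this. It concerns lung function and cyst features, matches work listed under Amendment 1 (February 2017), is nowhere expressed per flight, and came after the SAP of August 2015.

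**Size under the literal reading.** The share of events lost would be

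post-landing events ÷ all flight-related events.

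Neither count is in the documents, so the share could lie anywhere from 0% to 100%. As an illustration only, assume a constant hazard and flights of 2, 4 or 12 hours; neither assumption comes from the documents. The share kept is flight time ÷ (flight time + 24 hours):

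- 2 ÷ 26 = 8%
- 4 ÷ 28 = 14%
- 12 ÷ 36 = 33%

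These figures show that the two readings could differ widely. They are not an estimate. The mechanism described in the Protocol (Sections 1.2 and 3.0) is cyst expansion as pressure falls, which does not suggest equal risk through the flight and the following day.

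**The case for a change.** The strongest case for a change is that the text never equates the two terms. A SAP exists to settle the event in advance, and the illustration above shows that the wording could matter a good deal if taken at face value. The remedy would be cheap, since the defined term is the sponsor's own. The phrase 'associated with air travel' in the outcome measure carries no time window, so it does not close the gap by itself.

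The textual part of this stands: the terms differ, and one shared term would have been tidier. The harm does not follow. It needs an analyst to pass over the definition in the preceding sentence and to build an undefined outcome instead, and nothing in either document points that way.

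The side issues add no error. Keeping an operational definition in the SAP and out of the Protocol is ordinary practice, and nothing in the Protocol contradicts the window. The BHD title fits the staging in Protocol Section 3.0, where the BHD survey goes out first and the PLCH survey later. The documents do not show whether a separate PLCH plan exists, and nothing in them suggests a different window for those patients.

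**Conclusion.** No change is needed. This is a slip in terminology with an evident meaning: 'in-flight' stands for the flight-related event defined in the sentence before it. On that reading the rate and the risk-factor comparison cover the same events, and the effect on every result is zero.

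The conclusion rests on one assumption, that analysts apply the SAP's only event definition to both sentences. The order of the sentences, the lack of any announced subset and the air-travel wording of "To define the risk of pneumothorax related to air travel in patients with BHD and PLCH" all support it. If the assumption failed, the damage would be confined to an exploratory search for associated factors. The primary rate does not use the word, and its numerator is fixed in substance by the outcome-measures row. The loss in that case cannot be estimated from the documents.
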